Research Plan:

Study Design: Randomized, prospective, placebo-controlled, crossover trial

Population: PPI refractory GERD patients with at least 3 episodes of heartburn or reflux per week

Study Sites:

- Stanford Healthcare

Inclusion Criteria:

- Men and women aged >18.
- A minimum 6-month history of heartburn and regurgitation, as their main GERD symptoms.
- Experience at least 3 days with episodes of heartburn or regurgitation while on PPI therapy during the 7 days before randomization (run in period).
- PPI trial of at least one month. If not actively on PPI therapy they must be willing to restart therapy for the trial (a PPI that was used before).
- Need to be on PPI at least 1 week prior to starting the trial
- Female patients who are postmenopausal or using acceptable methods of birth control.

Exclusion Criteria:

- Current or historical evidence of the following GI issues:
 - Esophageal stricture
 - Primary esophageal motility disorder (per Chicago 3.0 classification), ok to have ineffective esophageal motility or fragmented peristalsis, but exclude all others (achalasia, EGJOO, jackhammer, absent peristalsis, distal/diffuse esophageal spasm)
 - Systemic sclerosis
 - Active inflammatory bowel disease
 - Zollinger-Ellison syndrome
 - Active gastric or duodenal ulcer
 - Active infectious or inflammatory conditions of the small or large intestine
 - Malabsorption syndromes
 - History of GI malignancy
 - Prior gastric or intestinal surgery
- Patients with significant co-morbidities including:
 - Decompensated cirrhosis
 - New York Heart Association class III or IV heart failure
 - Renal disease with GFR < 50
 - Pulmonary disease limiting activity or requiring oxygen
 - Malignancy
 - HIV infection
 - Significant psychiatric disease that would prevent participation in the study or accurate reporting of symptoms
 - Transplant
- Unable or unwilling to stop any anti-histamine drugs during the run in period
- Active drug or alcohol abuse
- Pregnancy or breast feeding
- Non-English speaking
- Unable or unwilling to give informed consent.
- Unable or unwilling to comply with study protocol for any reason

Intervention: Fexofenadine capsule 180 PO daily

Comparator: Identical placebo capsule

Trial Length: Total length 6 weeks: 1 week run-in, 2 weeks randomization to placebo vs fexofenadine, 1 week washout, 2 weeks crossover

Primary Outcomes: Mean percentage of GERD free days, Mean number of GERD episodes.

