Secondary Outcomes: Mean GERD-HRQL questionnaire score, Mean symptoms severity score (on a scale of 0-4), side effects, mean percentage of days on which rescue medications are needed, patient medication preference.

Statistical Considerations:

Sample Size: Sample size estimation was made referencing a trial evaluating GERD patients refractory to lansoprazole 30 mg daily. Patients in this trial were then randomized to treatment with lansoprazole twice daily or esomeprazole once daily. The mean percentage of GERD free days in the twice daily lansoprazole group was 57.5% (standard deviation 34.8%) (16). For the purposes of our trial with fexofenadine, we considered an additional 50% reduction in percentage of days with symptomatic GERD as a clinically significant endpoint (or mean percentage of GERD free days of 78.75%). Using alpha = 0.05 and beta 0.8 with paired means we calculated a needed sample size of 24 patients. *Our overall goal will be to recruit 40 patients to allow room for error.*

Data Analysis: We plan to analyze all data using a paired t-test comparing response to fexofenadine to response to placebo for each individual patient, provided data has a normal distribution. If not, then paired non-parametric analysis will be used. We will look specifically at the last week of treatment as we expect the drug to take a few days to build up to maximal effect. Drug preference will be compared using Fisher's exact test. Side effects will be compiled into a table to assess for major differences between fexofenadine and placebo.

Outline of key procedures/visits:

Recruitment:

Patients with potential proton pump refractory GERD will be contacted by phone or e-mail to assess interest, or recruited during office visits. Patients presenting to GI clinics will be pre-screened for potential recruitment. The decision to offer enrolment will be up to the treating physician. If the treating physician feels further workup or treatment is needed, then this should be done prior to initiation of the trial.

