Patients will complete an intake questionnaire which will be e-mailed to them via RedCap or secure e-mail, or they will complete the form in person in the office. This intake questionnaire will be reviewed by study staff to determine eligibility to start the run-in period. Prior to run in a subject ID number will be assigned, starting with 1 and increasing sequentially. If a patient presents to an office visit, they will be consented at that time with signatures. If they are contacted by phone/e-mail, they will be provided with the consent form and explanation of the study, but formal consent and signing of the consent forms will take place after the run-in period if they are candidates to continue the study (the run-in week of the study involves no intervention other than questionnaires and is minimal risk).

Run in period (1 week):

1. Patient will take proton pump inhibitor as previously prescribed.
2. Every night before bed patient will record both the number and severity (on a scale of 0-4) of the reflux episodes during the last 24 hours, and need for rescue medications (patients can only use Tums during this trial) in a diary that we provide.

3. On the last day of the period patient will fill out a GERD-HRQL questionnaire about symptoms during the last week.

We will assess by either phone or secure e-mail the number of days on which the patient had symptoms. If the patient had enough symptoms he/she will be invited to participate and to visit the office to sign consent if this was not done at an earlier time. At this point a randomization ID number will be assigned.

Office visit or phone/e-mail conversation (needs to be an office visit if consent has not been signed):

1. Study materials will be collected thus far.
2. Randomization will occur and first drug will be distributed either in person or by mail.

First randomization period (2 weeks):

1. Patient will take proton pump inhibitor as previously prescribed.
2. Patient will also take the study drug (either fexofenadine or placebo) in the morning.
3. Every night before bed patient will record both the number and severity (on a scale of 0-4) of the reflux episodes during the last 24 hours, and need for rescue medications (patients can only use Tums during this trial) in a diary that we provide.
4. On the last day of this period patient will fill out a GERD-HRQL questionnaire about symptoms during the last week.

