- Drugs will be stored at room temperature in a locked cabinet. Storage life is 6 months.
- During distribution a different staff member will distribute the drugs based on a randomization code that contains the subject ID number and the order of the drugs the patient will receive.
- After distribution, on the same randomization sheet the staff member will fill in the patient name, and date the drug is distributed. This will be stored in the same locked cabinet as the drugs.
- The randomization code will be kept by [name]
- We will not be perusing an IND, please see below
 - The IND Regulations [21 CFR 312.2(b)] state that clinical investigation of a drug product is exempt from the requirements for an IND if all of the following apply:
 - The Drug used in the investigation is lawfully marketed in the United States.
 - The investigation is not intended to be reported to FDA in support of new indication for use or to support any other significant change in the labeling for the drug.
 - The investigation is not intended to support a significant change in the advertising of the product.
 - The investigation does not involve a route of administration or dosage level, use in a participant population, or other factor that significantly increases the risks (or decreases the acceptability of the risks) associated with the use of the drug product.
 - The investigation is conducted in compliance with the requirements for IRB review and informed consent [21 CFR parts 56 and 50].
 - The investigation is conducted in compliance with the requirements concerning the promotion and sale of drugs [21 CFR part 312.7], e.g., the drug may not be represented as safe or effective for the purposes for which it is under investigation, nor may it be commercially distributed or sold.

Withdrawal from the study:

- Patients can be withdrawn for the following reasons
 - Side effect possibly related to the study drug
 - Failed adherence to study protocol
 - Discovery that the patient no longer meets inclusion or exclusion criteria
 - Other reasons after discussion with the other investigators

Safety Data:

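### The planned paired test has no period term, uses only patients with both periods, and no balancing of the two drug orders is described; a period-adjusted model with blocked sequences fixes this at almost no cost.

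*Combined protocol and SAP*

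**What the plan says.** The primary comparison is within patient: "We plan to analyze all data using a paired t-test comparing response to fexofenadine to response to placebo for each individual patient". If the data are not normal, "If not, then paired non-parametric analysis will be used. We will look specifically at the last week of treatment". Under Trial Length the schedule is "1 week run-in, 2 weeks randomization to placebo vs fexofenadine, 1 week washout, 2 weeks crossover", so the two analysed weeks are trial weeks 3 and 6. The Sample Size section derives 24 patients and then says "Our overall goal will be to recruit 40 patients to allow room for error", with no dropout rate. The Withdrawal section foresees patients leaving, but no rule covers a patient who has data from one period only.

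On allocation, the visit outline says "Randomization will occur and first drug will be distributed either in person or by mail", and the Drug Acquisition, Storage, and Distribution section refers to "a randomization code that contains the subject ID number and the order of the drugs the patient will receive". No ratio, blocking or other means of balancing the two orders is described.

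Two identifiers appear. In the visit outline, "Prior to run in a subject ID number will be assigned, starting with 1 and increasing sequentially"; after run-in, "At this point a randomization ID number will be assigned". The code is said to hold the first of these, and the text does not say when it is entered.

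**The concern.** In a two-period crossover, any change in symptoms between weeks 3 and 6 that is unrelated to treatment enters the fexofenadine-minus-placebo difference with opposite signs in the two sequences. It cancels only if the sequences are equal in size. If they are not, part of the time trend is reported as drug effect, in a direction set by which order has more patients. Even with equal sequences, the shift inflates the standard error of the paired test.

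The documents report no period effect, but the design leaves room for one. Patients are selected on at least 3 symptomatic days in a one-week run-in, which invites regression toward the mean. Patients who were off their PPI may restart it with only one week required before the trial. These are mechanisms; they say nothing about size.

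Separately, a test that needs both periods discards what a patient with only the first period has contributed.

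**Working it through.** **Inputs from the Sample Size section.** Effect 78.75 − 57.5 = 21.25 points; SD 34.8; alpha 0.05, taken as two-sided; target power 0.80. Using 34.8 as the SD of the paired difference amounts to assuming a within-patient correlation of 0.5, since 34.8 × √(2 × (1 − 0.5)) = 34.8.

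**The plan's own figure.** An exact paired t-test with these inputs has power 0.799 at 23 patients and 0.817 at 24. The stated 24 reproduces. At 40, power is 0.964.

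**Assumptions not in the documents.** Period shift (second period minus first) of 5, 10, 15 or 20 points; simple randomisation where a distribution of splits is needed; the dropout counts in the last step.

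**Bias of the paired mean.** The expected difference is 21.25 − shift in fexofenadine-first patients and 21.25 + shift in placebo-first patients, so

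bias = shift × (n placebo-first − n fexofenadine-first) / N.

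At 10 points: 16/8 gives 10 × 8/24 = 3.3; 26/14 gives 10 × 12/40 = 3.0. The sign follows the larger sequence. Under simple randomisation the mean absolute imbalance is 0.161 of N at 24 and 0.125 at 40, so the average absolute bias is 1.6 and 1.3 points. The chance of 16/8 or worse is 2 × P(Bin(24, 0.5) ≥ 16) = 0.152; of 26/14 or worse, 2 × P(Bin(40, 0.5) ≥ 26) = 0.081.

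**Error rates at a 10-point shift (simulation, 100,000 replicates per cell).**

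| Split | Paired type I error | Paired 95% CI coverage | Adjusted test |
|---|---|---|---|
| 16/8 | 0.064 | 0.937 | 0.05 / 0.95 |
| 26/14 | 0.072 | 0.928 | 0.05 / 0.95 |

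If the imbalance runs against the drug, paired power at 10 points falls to 0.65 at 16/8 and about 0.88 at 26/14, against 0.77 and 0.95 adjusted. If it runs the other way, apparent power rises, but through bias.

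**Power of the adjusted test.** The estimate is the mean of the two sequence means, with SE = (34.8/2) × √(1/n₁ + 1/n₂) and N − 2 degrees of freedom. At 12/12 the SE is 7.10 and power 0.816; at 20/20, 5.50 and 0.964; at 16/8, 7.53 and 0.769; at 26/14, 5.77 and 0.948.

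| Setting | Paired power at shift 5 / 10 / 15 / 20 | Adjusted, any shift |
|---|---|---|
| 12/12 | 0.81 / 0.79 / 0.76 / 0.72 | 0.816 |
| 20/20 | 0.96 / 0.96 / 0.95 / 0.93 | 0.964 |
| N=24, simple randomisation | 0.81 / 0.79 / 0.75 / 0.70 | 0.798 |
| N=40, simple randomisation | 0.96 / 0.95 / 0.93 / 0.90 | 0.960 |

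Averaged over simple randomisation, the paired test's type I error is 0.050.

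**Non-parametric fallback.** GERD-free days over 7 days take only eight values. They were simulated (4,000 replicates per cell) with means 57.5% and 78.8% and correlation 0.46; 22% of placebo weeks and 47% of fexofenadine weeks were fully symptom-free. With a 10-point shift and a 16/8 split in either direction, type I error was 0.063–0.069 for the paired t-test and 0.061–0.064 for signed-rank. Over all splits and shifts tried, a rank-sum test of period differences between sequences gave 0.044–0.055 and the adjusted t-test 0.046–0.053. Power at 12/12 and shift 10 was: paired t 0.80, signed-rank 0.79, adjusted t 0.815, rank-sum 0.805. The episode count was not simulated.

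**One-period patients.** For 40 randomised, data missing at random and correlation 0.5, a random-intercept model with estimated variance components has variance 0.95 of the completers-only analysis with 32 complete and 8 first-period-only (power 0.93 against 0.92). With 24 and 16 it is 0.90 (0.85 against 0.82). For correlations 0.3 to 0.7 the ratios run 0.93–0.97 and 0.88–0.94.

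**The case against.** The harm needs two things that the documents do not show: a period effect and an unequal split. A 10-point shift is 47% of the whole target effect (10/21.25), and the paired test is valid on average over randomisation. With equal sequences it errs only on the conservative side (type I error about 0.04 at a 10-point shift). Blocking alone would remove most of the bias, after which the paired test at 20/20 loses under 1 power point for shifts up to 10. The code may already be balanced and simply not described. The gain from one-period patients is small, rests on invented dropout counts and on missingness at random, and disappears if the rank-based fallback applies.

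Most of this stands and keeps the point at minor to moderate. It does not remove it. The trial reports one realised split, and its estimate and interval should be right for that split. Blocking balances those randomised, not those who complete, and it leaves the period variance in the paired standard error: at 12/12 with a 20-point shift, power is 0.72 against 0.816. Adjustment does cost power when the split is unequal and there is no shift, which is a reason to block as well. If the code is already balanced, one sentence settles that part.

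**Conclusion.** The point holds as a worthwhile improvement, not as an invalid analysis. The main gain is an estimate and interval free of bias given the split that occurs: about 3 points of bias at a 10-point shift and a split as uneven as 16/8 or 26/14, and 1.3 to 1.6 points on average under simple randomisation. Power is a lesser argument. Without blocking, the adjusted test is slightly weaker than the paired test at a 5-point shift, about 1 point better at 10, and materially better only from about 15. Using one-period patients is a modest second benefit.

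These sizes rest on an SD of differences of 34.8, an assumed shift and, for the averages, simple randomisation. They cover GERD-free days only. A period term does not deal with carry-over. The two identifiers need reconciling; no harm is claimed from that discrepancy.

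**What to change.** - **Primary analysis.** Use a linear mixed model with fixed treatment, period and sequence and a random patient effect, fitted by restricted maximum likelihood with small-sample degrees of freedom. Include every randomised patient with last-week diary data in at least one period, and state the missing-at-random assumption. Keep the paired test as a sensitivity analysis.
- **Fallback.** If normality fails, compare within-patient period differences between the two sequences by rank-sum test. State that this adjusts for period but still needs both periods.
- **Allocation.** Assign the two orders 1:1 in permuted blocks keyed to the randomization ID given after run-in, so that run-in failures leave no gaps in the blocks. Reconcile the visit outline with the drug distribution section on which ID the code uses.

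The cost is a few lines of SAP text, one line on the list and one degree of freedom: power goes from 0.817 to 0.816 at 12/12 and from 0.9645 to 0.9643 at 20/20. Adopt the model and the blocking together. With the model alone and no period effect, average power under simple randomisation falls from 0.818 to 0.798 at 24 patients and from 0.964 to 0.960 at 40; at 16/8 it falls from 0.82 to 0.77 and at 26/14 from 0.96 to 0.95. The rank-sum fallback costs about 1 power point against the adjusted t-test. No extra patients or visits are needed.

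### Remote recruits sign consent only after run-in because run-in is described as questionnaires only, yet the plan also requires antihistamines to be stopped and rescue limited to Tums in that week

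*Combined protocol and SAP*

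**What the plan says.** Consent depends on the route of recruitment (Outline of key procedures/visits, Recruitment). Patients seen in the office sign at that visit. For those reached by phone or e-mail, "formal consent and signing of the consent forms will take place after the run-in period", and then only "if they are candidates to continue the study". What these patients get before run-in is information: "they will be provided with the consent form and explanation of the study". The stated ground for the delay is that "the run-in week of the study involves no intervention other than questionnaires and is minimal risk".

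Two other places set conditions on medicines in that same week:

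- The Exclusion Criteria remove anyone "Unable or unwilling to stop any anti-histamine drugs during the run in period".
- Step 2 of the run-in procedures, in the sentence on recording rescue use, states that "patients can only use Tums during this trial".

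After run-in, staff count the symptom days: "If the patient had enough symptoms he/she will be invited to participate and to visit the office to sign consent", unless a signature is already on file. The threshold is in the Inclusion Criteria: "Experience at least 3 days with episodes of heartburn or regurgitation while on PPI therapy during the 7 days before randomization (run in period".

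**The concern.** The plan gives two grounds for letting remote recruits go through run-in before formal consent: that the week contains only questionnaires, and that it is minimal risk. If the first is untrue for some patients, the deferral rests on an incomplete account of what they are asked to do. A patient who takes a daily antihistamine for allergy would have to give it up for the sake of the study before consenting formally. If that patient then has too few symptom days, the plan provides no occasion to sign at all.

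What is at stake is participant protection and the accuracy of the plan's description of run-in, on which anyone approving the deferral would rely. The treatment comparison is not at stake, because only patients who have signed are randomized.

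**Working it through.** There is no planned figure to reproduce. The check sets the provisions side by side.

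**1. Is run-in part of the trial?** Yes. Trial Length counts it as the first of six weeks. A subject ID is assigned before it begins, and a daily diary and a GERD-HRQL are completed during it. It is more than a pre-screening call.

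**2. Does the plan require a medication change in that week?**

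| Condition | Where | Tied to run-in? | Weight |
|---|---|---|---|
| Stop antihistamines | Exclusion Criteria | Yes, run-in is named | Main support |
| Tums as the only rescue | Run-in step 2 | Yes, printed among the run-in steps | Milder: limits as-needed use |
| Restart a lapsed PPI | Inclusion Criteria | Timing relative to signing is not clear | Weak: some restarts may be ordinary care |

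The first row is enough to contradict a description of run-in as questionnaires only. The second adds a little. The third is noted, but nothing is built on it and no duration is claimed for it.

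**3. Does the change come before formal consent?** For remote recruits, yes. The antihistamine stop belongs to run-in and signing follows run-in. Run-in is 1 week × 7 days = 7 days. No stop day is given, so the supported statement is up to 7 days.

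**4. Who is not asked to sign?** Entry needs at least 3 symptom days out of 7. A remote recruit with 0, 1 or 2 is not invited to the signing visit. These counts define who fails. They say nothing about how often failure occurs, and the documents give no rate.

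**5. Who is affected?** Remote recruits who take an antihistamine or would otherwise use a rescue medicine other than Tums. Their number is not given. Antihistamine users are foreseeable, since the plan has a criterion for them.

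**The case against.** The strongest defence is that the word intervention means study treatment. The Research Plan uses it as the heading for the fexofenadine capsule, and no study capsule is taken during run-in. On that reading the sentence is merely incomplete. This does not quite work, because the sentence itself counts questionnaires as an intervention, so it is plainly using the word more broadly.

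A second defence is that the antihistamine stop appears only as an eligibility criterion and none of the run-in steps instructs it. That is true, and it is why the 7 days are a ceiling. But the criterion names the run-in period, and stopping in that period is its natural meaning.

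Other parts of the defence stand. The minimal-risk ground is not disputed. Remote recruits are informed before they start. Signing comes before randomization and before any study drug. The consent pages and the ethics board's decision are not in view, so the medication conditions may have been disclosed there, or a waiver of signature granted.

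A reader might go further and infer that consent is never obtained from remote run-in failures, or that consent rules or the IND-exemption conditions listed under Drug Acquisition, Storage, and Distribution are breached. The documents support neither. They show only that formal, signed consent is not taken from these patients, after the form and an explanation have been provided. The absence of a waiver from this text does not show that none exists.

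**Conclusion.** The point holds as a minor participant-protection matter. One of the two reasons given for deferring formal consent is inaccurate, because run-in carries an antihistamine stop and, less importantly, a limit on rescue medication. As written, a remote recruit on an antihistamine would make a research-driven medication change lasting up to 7 days before formal consent, and with fewer than 3 symptom days would never be asked to sign.

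This rests on reading the exclusion criterion as requiring the stop within run-in, and on the deferral operating as described with no alternative arrangement recorded elsewhere. The risk to any one patient is probably low and the number of patients is unknown. Nothing here bears on the estimate of fexofenadine's effect.

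**What to change.** Staff already review an intake questionnaire before run-in. Use that review to identify remote recruits who must stop an antihistamine or change another medicine for the study, adding items on antihistamines and rescue medicines if the form lacks them. Take their formal consent before the change, by office visit, by mail, or by electronic signature if the ethics board approves one. Whether remote recruits who need no change may still sign after run-in can be left to the board.

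Replace the sentence describing run-in with its actual conditions: diary and questionnaires, continued PPI use, no antihistamines, and Tums as the only rescue medicine. If the board has already granted a waiver, the protocol should say so.

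The cost is one amendment, plus an earlier visit, mailing or approved electronic signature for the affected patients. The downside is that some consent effort will go to people who then fail run-in. Office recruits already sign before run-in, so the change brings the affected remote recruits to the same standard.
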